### ***2.1.3.3 Other efficacy endpoints***

- First occurrence of CV death, HHF, or urgent visit for HF
- First occurrence of CV death or HHF
- Total occurrences (first and potentially subsequent) of HHF after randomization
- Total occurrences (first and potentially subsequent) of urgent HF visits after randomization
- First occurrence of CV death, HHF, urgent visit for HF, non-fatal myocardial infarction, and non-fatal stroke
- First occurrence of fatal and non-fatal MI
- First occurrence of fatal and non-fatal stroke
- First occurrence of new onset of atrial fibrillation or atrial flutter (adverse events (AEs) with a preferred terms (PTs) of atrial fibrillation or atrial flutter)
- First occurrence of a composite renal endpoint, consisting of events sustained  $\geq 50\%$  decrease in eGFR from baseline (for  $\geq 30$  days), chronic dialysis, renal transplant, or sustained eGFR  $< 15$  mL/min/1.73m^2 (for  $\geq 30$  days)
- First occurrence of severe hypoglycemia
- Total occurrences of the following hypoglycemia categories
  - Severe hypoglycemia
  - Hypoglycemia with documented glucose value  $< 54$  mg/dL
  - Hypoglycemia with documented glucose value  $< 70$  mg/dL
- Days alive and out of hospital (DAOH) and percent DAOH (PDAOH)

- Changes from baseline in NT-proBNP, hematocrit, HbA1c, body weight, and SBP

All time-to-event endpoints are assessed based on investigator-reported events.

Cardiovascular death includes death of undetermined cause.

The first occurrence of the composite renal endpoint is defined as follows:

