### **2.3.2 Efficacy population**

The efficacy analysis population will be the ITT population, consisting of all randomized patients.

Patients in the ITT population will be analyzed according to the treatment group allocated by randomization.

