#### ***2.4.4.4 Additional efficacy analysis(es)***

Time-to-event other efficacy endpoints will be analyzed using the same statistical methodology as for the primary endpoint. If the endpoint concerns the first event, then only the first event experienced by a given patient will be included in the analysis. Deaths that are not part of a given endpoint will be treated as competing events.

For the analyses of DAOH and PDAOH, total potential follow-up time for each patient is defined as the number of days from date of randomization until the patient's date last known alive, or May 1, 2020 (the date sites were instructed to complete end of study contacts with patients; patients known to have died after this date will be censored as alive as of May 1, 2020) if the patient died. The total number of days spent in hospital will be derived from the investigator reports. If a patient died, the number of days dead will be calculated as the time interval between their date of death and May 1, 2020. DAOH will be calculated by subtracting days in hospital and days dead from total potential follow-up time; if a patient survived without hospitalization, DAOH will be equal to the potential follow-up time for that patient.

DAOH, days dead, and days in hospital will be compared between treatment groups by rate ratios (RRs) from a Poisson regression model with a log link function and Pearson  $\chi^2$  scaling of standard errors to account for potential overdispersion. In addition to treatment group, the logarithm of potential follow-up time will be used as an offset variable in the model. Given the expectation that a fraction of patients will survive without hospitalization until the end of follow-up (i.e., PDAOH =100%), PDAOH will be compared between treatment groups with one-inflated beta regression. In this application, the model will jointly estimate the treatment odds ratio (OR) of surviving until the end of the study without hospitalization (ie, PDAOH =100%), and the treatment OR of higher mean PDAOH among the subset of patients who died or had at least one hospitalization or died during follow-up (i.e., PDAOH <100%). Plots of the distribution of DAOH will be constructed,

as well as summaries of reasons for hospitalizations (e.g., HF, other efficacy event, non-efficacy adverse event, etc.).

Changes from baseline in NT-proBNP, hematocrit, HbA1c, body weight, and SBP will be analyzed using the same methods as for change in eGFR.

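### The second odds ratio in the PDAOH model compares arms only among patients who died or were hospitalized, so it is not a randomized comparison, and the model has no place for PDAOH = 0

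*SAP*

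**What the plan says.** PDAOH is listed in SAP 2.1.3.3 among the other efficacy endpoints. The fixed testing order in SAP 2.4.4.3 covers the primary and the secondary endpoints only. On population, SAP 2.3.2 states: "The efficacy analysis population will be the ITT population, consisting of all randomized patients".

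SAP 2.4.4.4 defines the measure and two analyses.

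- Definition: "DAOH will be calculated by subtracting days in hospital and days dead from total potential follow-up time". For a patient who died, "the number of days dead will be calculated as the time interval between their date of death and May 1, 2020".
- DAOH: "DAOH, days dead, and days in hospital will be compared between treatment groups by rate ratios (RRs) from a Poisson regression model", with the log of potential follow-up as offset and Pearson scaling of the standard errors.
- PDAOH: "PDAOH will be compared between treatment groups with one-inflated beta regression". In its first part, "the model will jointly estimate the treatment odds ratio (OR) of surviving until the end of the study without hospitalization". Its second part gives an odds ratio for "higher mean PDAOH among the subset of patients who died or had at least one hospitalization", that is, patients with PDAOH below 100%.

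The section does not combine the two odds ratios into one PDAOH effect and does not say how to read them if they disagree. It gives no rule for PDAOH = 0 and does not say whether days of the index admission after randomization count as hospital days.

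**The concern.** The subset in the second part is defined by the outcome. Randomization balances the arms at entry, not among those who later die or are admitted. When a drug prevents an admission in a patient who survives, that patient leaves the subset. Such patients usually have PDAOH close to 100%, so their departure lowers the treated subset's mean even though nobody has fared worse.

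The case is not remote. SAP Appendix D says that DAOH and PDAOH were added to show the relevance of fewer hospitalizations, and a drug that acts mainly on hospitalizations is the one for which this odds ratio can point the wrong way. At stake is a prespecified efficacy estimate that could be reported as evidence of harm, or of no effect, for a drug that increases time alive and out of hospital.

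The second gap is technical. A one-inflated beta distribution covers values above 0 up to and including 1. A patient who spends no day alive and out of hospital has PDAOH = 0, which the model cannot accommodate.

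**Working it through.** The documents give no figure for PDAOH, so there is nothing to reproduce. All rates below are assumptions chosen to show direction and range.

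**Arithmetic example.** Assume 600 patients per arm. On placebo, 100 die (mean PDAOH 0.50), 200 survive with at least one hospitalization (mean 0.96), and 300 have PDAOH = 100%.

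- Subset mean = (100 × 0.50 + 200 × 0.96) / 300 = 242 / 300 = 0.807.
- Overall mean = P(100%) + [1 − P(100%)] × subset mean = 0.500 + 0.500 × 0.807 = 0.903.

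Now let the drug prevent 40% of the hospitalized-survivor cases and no deaths, leaving 120 hospitalized survivors and 100 deaths.

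- P(100%) = 380 / 600 = 0.633. First odds ratio = (0.633 / 0.367) / (0.500 / 0.500) = 1.73.
- Subset mean = (50 + 115.2) / 220 = 0.751. Second odds ratio, on the means = (0.751 / 0.249) / (0.807 / 0.193) = 0.72.
- Overall mean = 0.633 + 0.367 × 0.751 = 0.909, up from 0.903.

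The same formulas for other mixes, each against the placebo arm above:

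| Drug effect | Hospitalized survivors / deaths | First OR | Subset mean | Second OR | Overall mean |
|---|---|---|---|---|---|
| Hospitalizations −40% | 120 / 100 | 1.73 | 0.751 | 0.72 | 0.909 |
| Hospitalizations −40%, deaths −10% | 120 / 90 | 1.86 | 0.763 | 0.77 | 0.917 |
| Both −25% | 150 / 75 | 1.67 | 0.807 | 1.00 | 0.9275 |
| Deaths −25% only | 200 / 75 | 1.18 | 0.835 | 1.21 | 0.924 |

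Every row is a benefit overall. The second odds ratio runs from 0.72 to 1.21 according to the mix.

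**Simulated trials with the models fitted.** There were 400 trials of 600 per arm, follow-up 90-640 days, 16.7% deaths in both arms, and hospitalized survivors 33.3% on placebo and 20% on drug. The median first odds ratio was 1.72, significantly in favor in over 99% of trials. The median second odds ratio was 0.83, below 1 in 99% and significantly against the drug in 44%. Mean PDAOH over all patients was 0.49 points higher on drug, and the median Poisson rate ratio for DAOH was 1.004.

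**Simulation with event rates.** Deaths were 0.18 per year and hospitalizations 0.8 per year, with 8-day stays, follow-up of 2-21 months, and frailty variance 0, 1 or 2.

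- Hospitalizations cut 30%, deaths unchanged: second odds ratio 0.90-0.92, first 1.24-1.44, overall mean PDAOH up 0.4-0.5 points.
- Hospitalizations cut 40%, deaths unchanged: second odds ratio 0.85-0.89.
- Hospitalizations cut 30% and deaths 15%: second odds ratio 0.99-1.02, overall mean up 1.4-1.6 points.

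A further simulation with similar rates gave a second odds ratio of 0.94-0.97 for cuts of 30-40% with deaths unchanged, and an overall gain of 0.4-0.8 points. With deaths unchanged, the direction is the same in all runs; the size is not.

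**PDAOH = 0.** Take a patient randomized in hospital 200 days before May 1, 2020, who dies there after 20 days. DAOH = 200 − 20 − 180 = 0. Protocol 6.1.2 allows randomization before discharge, and SAP Appendix D records that Amendment 2 allowed enrollment on the first day of hospitalization. The beta log-density at 0 was minus or plus infinity depending on the parameters, and a trial fit with one zero in the data failed.

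**The case against.** A reader might infer that the whole PDAOH model is confined to the died-or-hospitalized subset, so that a drug preventing admissions would simply look harmful. The documents do not support that. The first odds ratio uses all randomized patients and would show the prevented admissions. The planned output would be two discordant odds ratios.

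A reader might also infer that the plan gives no overall effect on time alive and out of hospital. It does give one. With treatment as the only covariate and log follow-up as offset, the Poisson rate ratio for DAOH is (total DAOH / total potential follow-up) on drug divided by the same quantity on placebo. It covers all randomized patients and accepts both 0 and 100%. In the arithmetic example, with equal follow-up in every patient, it would be 0.909 / 0.903, about 1.006, in the favorable direction. The separate rate ratios for days dead and days in hospital would help explain a contrary second odds ratio.

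Further, the SAP openly labels the subset, the reversal needs a drug that acts on admissions much more than on deaths, and zeros are likely to be few, since protocol 7.1.2 requires hemodynamic stability and no intravenous diuretic at randomization. Nor does the SAP say that zeros would be excluded, so it cannot be asserted that the worst outcomes drop out.

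All of this stands, and it limits the point. It does not turn the second odds ratio into a randomized comparison, supply a per-patient PDAOH contrast over everyone randomized, or say what happens to a zero.

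**Conclusion.** The point holds for the second part of the PDAOH model only. That odds ratio conditions on a post-randomization outcome and cannot be read as a treatment effect. Under the assumed rates it was about 0.72-0.97 when hospitalizations fell 30-40% with deaths unchanged, about 1 when both fell by 25% (or by 30% and 15%), and 1.21 when only deaths fell. These figures rest on assumptions about event rates, length of stay and timing of death that the documents do not supply. The direction of the problem is more certain than its size.

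The missing rule for PDAOH = 0 is a real but narrow gap. The silence on index-admission days matters a little more. If those days count, a patient randomized before discharge cannot reach PDAOH = 100%, and the first odds ratio no longer measures survival without a new hospitalization. If they do not count, zeros are rarer but still possible, for example with death on the day of randomization.

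The impact is minor. PDAOH is outside the testing hierarchy, and no primary or secondary conclusion depends on it.

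**What to change.** In SAP 2.4.4.4:

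1. Define the PDAOH treatment effect as the between-arm difference in mean PDAOH over all randomized patients, with a bootstrap or robust confidence interval. This accepts 0 and 100% and reads in percentage points.
2. Keep the odds ratio for PDAOH = 100%.
3. Label the subset odds ratio descriptive and not a treatment effect, or drop it.
4. If the beta model is kept, state a boundary rule for PDAOH = 0. A zero-inflation component is an alternative but could be unstable with very few zeros.
5. State whether days of the index admission after randomization count as days in hospital.

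The cost is a few sentences and a short program. No new data are needed, and the Poisson analyses stay as they are.

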In Study LX4211.1 202 DM (40) sotagliflozin induced a dose-dependent increase of hematocrit, albumin, and hemoglobin. The mean change (standard deviation [SD]) in hematocrit from Baseline to Week 12 was 0.9% (2.52), 2.0% (2.47), and 1.9% (2.78) in patients receiving sotagliflozin 200 mg qd, 200 mg bid and 400 mg qd, respectively versus -0.5 (2.98) % in the placebo arm. The mean change (SD) in albumin from Baseline to Week 12 was 0.0 (0.279), 0.09 (0.243) and 0.12 (0.242) g/dL in patients receiving sotagliflozin 200 mg qd, 200 mg bid and 400 mg qd, respectively versus (0.273) -0.04 g/dL in the placebo arm. The mean change (SD) in hemoglobin from Baseline to Week 12 was 0.29 (0.775), 0.55 (0.688) and 0.60 (0.820) g/dL in patients receiving sotagliflozin 200 mg qd, 200 mg bid and 400 mg qd, respectively versus -0.19 (1.084) g/dL in the placebo arm. In addition, in the same study, a prespecified sub-analysis of patients with a Baseline BP  $\geq$ 130 mmHg showed that systolic BP decreased by 7 and 14 mmHg (placebo-subtracted), respectively, in the 200 mg qd and 400 mg qd groups.

Therefore, given the observed higher efficacy of the 400 mg dose on glycemic control, hemoconcentration, and BP reduction, and given the potential benefit of these changes on cardiovascular outcomes, the dose of 400 mg was chosen as the proposed maintenance dose for the study.

Sotagliflozin induces an acute, but modest, decrease in estimated glomerular filtration rate (eGFR). Since the study population includes patients at increased risk of acute kidney injury (ie, patients with moderately impaired renal function), study treatment will begin with the low dose of sotagliflozin (200 mg qd) and will be increased to the maintenance dose of 400 mg qd, once tolerability of the low dose has been established by the Investigator.

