### **9.1.3 Other efficacy endpoints**

All the following endpoints are assessed in the total patient population:

- Proportion of patients with HHF or urgent HF visit (see [Appendix B](#)) within 30 days of Randomization
- Changes in KCCQ-12 scores from Baseline to Week 2, Month 1, Month 4, Month 8, Month 12, then annually
- Time to  $\geq 50\%$  decrease in eGFR from Baseline
- Proportion of patients with  $\geq 1$  new onset of atrial fibrillation, atrial flutter, or ventricular arrhythmia from Randomization
- Time to first MI (fatal and nonfatal)
- Time to first stroke (fatal and nonfatal)
- Changes from Baseline to Month 1 and Month 4 for NT-proBNP
- Changes from baseline in loop diuretics at day 180 and/or end of treatment visit
- Changes in hemoconcentration from Baseline at Week 2, Month 1, Month 4, Month 12, and EOT
- Changes from Baseline to Month 4, Month 12, and Month 24 in:
  - Hemoglobin A1c
  - Body weight

- Time to first occurrence of either of the following clinical events in subgroups of patients who started first IMP dose prior vs. after hospital discharge (or urgent care facility where appropriate):
  - Cardiovascular death
  - Hospitalization for heart failure

The following endpoints are assessed in subgroups of patients defined by LVEF:

- Time to first occurrence of either of the following clinical events in patients with LVEF <40%:
  - Cardiovascular death
  - Hospitalization for heart failure
- Time to first occurrence of either of the following clinical events in patients with LVEF  $\geq$ 40% to <50%:
  - Cardiovascular death
  - Hospitalization for heart failure
- Time to first occurrence of either of the following clinical events in patients with LVEF  $\geq$ 50%:
  - Cardiovascular death
  - Hospitalization for heart failure
- Time to all-cause mortality in patients with LVEF <40%
- Changes in hemoconcentration from Baseline at Week 2, Month 1, Month 4, Month 12, and EOT in patients with LVEF <40%

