#### **11.4.2.3 Other endpoints**

Other time to event endpoints will be analyzed using the same stratified Cox proportional hazards model described for the second primary endpoint with LVEF and region (North America, Latin America, Western Europe, Eastern Europe, and rest of the world) as stratification factors and treatment as fixed effect factor. The LVEF will not be included in the statistical model as stratification factor if the endpoint is defined in a subgroup of patients by LVEF, eg, LVEF<40%.

Number (%) of patients with at least 1 new onset of atrial fibrillation, atrial flutter, or ventricular arrhythmia since Randomization will be summarized by treatment group. For other endpoint of changes in concomitant loop diuretic medications, summary tables will be provided.

Analysis of other endpoints will be descriptive with no statistical testing. Summary statistics at scheduled visits using observed data will be provided by treatment group. Graphical presentations will also be used to illustrate trends over time if applicable.

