#### ***2.4.4.2 Analyses of secondary efficacy endpoints***

Methods for controlling the overall type-I error rate when testing the secondary efficacy endpoints are described in Section 2.4.4.3 *Multiplicity issues*.

Time-to-event secondary efficacy endpoints will be analyzed using the same statistical methodology as for the primary endpoint. Deaths that are not part of a given endpoint will be treated as competing events.

As with the primary endpoint, the absolute risk reduction (ARR) of time-to-event secondary endpoints will be estimated by the difference between treatment groups in the number of events per 100 patient-years of follow-up. For those secondary endpoints which are a composite of events, results will be provided for both the overall composite and its individual components.

Absolute change in KCCQ-12 scores from baseline to Month 4 will be analyzed by analysis of covariance (ANCOVA) with treatment group as factor and baseline KCCQ-12 score and randomization stratification factors as covariates. The last available post-baseline score will be

carried forward to Month 4 if the patient is alive at Month 4 but the Month 4 value is missing. For patients who die, a worst score (0) will be imputed for the clinical summary score at all subsequent scheduled visits after the date of death where the clinical summary score would have been assessed.

The rate of decline in eGFR observed over time will be analyzed by repeated-measures mixed-effects models with absolute change in eGFR from baseline as the outcome, a random effect for intercept, and fixed effects for treatment, baseline value, and time. An additional model will be developed with an interaction between treatment and time. The variance-covariance matrix will be specified to be unstructured.

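### Change in NT-proBNP, hematocrit, HbA1c, weight and SBP goes through the eGFR rate-of-decline method, with no time point and no stated contrast to report

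*SAP*

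**What the plan says.** Protocol 9.1.3 ties four of these markers to named times:

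- NT-proBNP: "Changes from Baseline to Month 1 and Month 4 for NT-proBNP".
- Hemoconcentration, which the SAP renders as hematocrit: "Changes in hemoconcentration from Baseline at Week 2, Month 1, Month 4, Month 12, and EOT".
- HbA1c and body weight: "Changes from Baseline to Month 4, Month 12, and Month 24 in" each.

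Protocol 11.4.2.3 plans these endpoints as descriptive, without testing: "Summary statistics at scheduled visits using observed data will be provided by treatment group". SBP is not a protocol efficacy endpoint.

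SAP 2.1.3.3 lists only "Changes from baseline in NT-proBNP, hematocrit, HbA1c, body weight, and SBP", with no time point. SAP 2.4.4.4 then says "Changes from baseline in NT-proBNP, hematocrit, HbA1c, body weight, and SBP will be analyzed using the same methods as for change in eGFR". The eGFR method in SAP 2.4.4.2 is a mixed model with a random intercept and "fixed effects for treatment, baseline value, and time", followed by an additional model that adds treatment by time. It serves the secondary endpoint in SAP 2.1.3.2, a yearly rate of eGFR decline after Week 4. SAP 1.1 states that the SAP prevails over the protocol where they differ. Appendix D, the list of key changes, mentions neither the loss of the time points nor the addition of SBP.

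**The concern.** The protocol asks how far each marker has moved by a stated visit. The SAP borrows a method built for a different question, the yearly rate of change of eGFR. The main model has no interaction, so it returns one treatment effect pooled over every visit a patient reached.

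The markers most exposed are those sampled from Week 1, because Weeks 1 and 2 fall before the scheduled up-titration. The protocol itself reports that "sotagliflozin induced a dose-dependent increase of hematocrit, albumin, and hemoglobin". In a trial closed early, a pooled effect also depends on how long patients were followed.

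At stake is the interpretability of five supportive endpoints. The analyst would also have to choose the form of time, the coefficient to report and the start of follow-up after the SAP is final.

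**Working it through.** The documents give no figure for these endpoints, so there is none to reproduce.

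**1. Time points and first samples** (Protocol 9.1.3; flow chart 1.2; visit lists in 10.1.2)

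| Marker | Protocol time points | SAP time point | First post-baseline value |
|---|---|---|---|
| NT-proBNP | Months 1, 4 | none | Week 4 |
| Hematocrit | Week 2, Months 1, 4, 12, EOT | none | Week 1 |
| HbA1c | Months 4, 12, 24 | none | Month 4 |
| Body weight | Months 4, 12, 24 | none | Week 1 |
| SBP | not an efficacy endpoint | none | Week 1 |

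**2. What each model returns**

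- Main model: one treatment coefficient, a weighted mean of the visit-specific differences. This is so whether time is continuous or categorical, because there is no interaction.
- Second model, continuous time: difference at time t = b0 + b1·t, a straight line. The slope b1 measures divergence, not the size of a sustained effect.
- Second model, categorical time: a separate difference at each visit. This would answer the protocol's question, but the SAP does not say that it is meant.

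**3. Illustration for hematocrit**

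Protocol 4.4.1 gives Week 12 changes of -0.5 (placebo), 0.9 (200 mg qd) and 1.9 (400 mg qd).

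- Placebo-corrected effects: 0.9 - (-0.5) = 1.4; 1.9 - (-0.5) = 2.4.
- Assumptions: these effects apply at once, 200 mg at Weeks 1 and 2, 400 mg from Week 4, with equal visit weights.
- Visits to Month 8 (Weeks 1, 2, 4, Months 4, 8): (2×1.4 + 3×2.4)/5 = 2.0, and (2.4 - 2.0)/2.4 = 17% lower.
- Visits to Month 4 (Weeks 1, 2, 4, Month 4): (2×1.4 + 2×2.4)/4 = 1.9, and (2.4 - 1.9)/2.4 = 21% lower.

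**4. The same case with a start after Week 4**

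Only visits at 2.4 remain. The average is 2.4, so the dilution is gone. A continuous-time slope difference is 0, although the effect is 2.4 throughout.

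**5. Sensitivity to onset and follow-up**

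Expected coefficients of the main model on the protocol visit schedule, all visits included. Assumed effect: 1 - exp(-t/τ), plateau 1. Assumed intraclass correlation: 0.3 or 0.6. Assumed follow-up: uniform 1.5 to 12 months, uniform 1.5 to 22 months, or 24 months for all.

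| τ (weeks) | True Month 4 effect | Hematocrit, weight, SBP average | Below Month 4 | NT-proBNP average | HbA1c average |
|---|---|---|---|---|---|
| 1 | 1.00 | 0.87–0.94 | 6–13% | 0.99–1.00 | 1.00 |
| 4 | 0.98 | 0.56–0.80 | 18–43% | 0.80–0.90 | 0.99–1.00 |
| 8 | 0.86 | 0.41–0.73 | 15–52% | 0.64–0.81 | 0.90–0.97 |

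Within a row, the hematocrit, weight and SBP range comes almost wholly from follow-up length. The documents give neither the onset curve, nor the correlation, nor the follow-up distribution.

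**The case against.** The case on the other side is substantial.

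- **The model may already be adequate.** SAP 2.4.4.2 speaks of repeated measures and an unstructured covariance matrix, and SAP 2.5.4 applies its time windows to all analyses. With categorical time, the second model gives visit contrasts. Even with continuous time it yields a fitted difference at any month, possibly misspecified. A reader might infer that no time-point difference could be obtained at all; the text does not support that. What stands is that the SAP leaves this open, and that the main model averages on either reading.
- **Not all five markers are affected alike.** A reader might infer dilution throughout. HbA1c and NT-proBNP have no Week 1 or 2 samples, so their averages do not mix in those visits. NT-proBNP is diluted only if its effect builds slowly.
- **The two failures do not occur together.** Dilution needs the early visits in the model; a zero slope for a reached plateau needs them out.
- **The protocol promised no between-group estimate here.** It planned by-visit description, though its objectives in 5.3 are worded as comparisons. By-visit summaries survive in SAP 2.4.5.2 for hematology. They apparently survive in 2.4.5.3 for weight and SBP, although that paragraph says laboratory variables. Both use the safety population, and SAP 2.1.4.2 does not name NT-proBNP or HbA1c.
- **No time course is documented.** Protocol 4.4.1 gives 12-week values, and the early effect in Protocol 4.2 concerns urinary glucose. The early-plateau premise is therefore an assumption.

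**Conclusion.** The point holds as a gap in specification with a mismatched default. The governing SAP drops the protocol's time points, and its main model reports a whole-follow-up average. The form of time, the reported coefficient and the start of follow-up are unstated, and Appendix D is silent.

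The 17 to 21% shortfall for hematocrit is an illustration, not a forecast. It rests on Week 12 effects applied from the first visit, equal visit weights, and early visits entering the model. The wider 6 to 52% range for hematocrit, weight and SBP rests on the assumed onset curves and follow-up.

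A reader might infer that the trial's conclusions are at risk. They are not: these endpoints sit outside the testing hierarchy of SAP 2.4.4.3, so type I error and the primary and secondary results are untouched. This is a cheap and worthwhile improvement, not a fault in the main analysis.

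**What to change.** In SAP 2.4.4.4, replace the reference to the eGFR method for these markers with a mixed model containing treatment, categorical visit (using the 2.5.4 windows), treatment by visit, and baseline value. Report between-group differences at:

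- NT-proBNP: Months 1 and 4.
- Hematocrit: Week 2 and Months 1, 4 and 12. End of treatment falls at different times in different patients, so it is better summarized separately.
- HbA1c and body weight: Months 4 and 12, and Month 24 if enough patients reach it.
- SBP: by visit, since the protocol sets no time point.

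State that the slope model and the start after Week 4 apply to eGFR only. Record the change, including the addition of SBP, in Appendix D.

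The cost is a few lines of SAP text and one reprogrammed model. Each visit contrast will be slightly less precise than an average over all visits. If data are missing at random, it estimates the effect at that visit whatever the length of follow-up.
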